9.4 Statistical Analyses of Primary Endpoint

Safety analyses will be performed in all treated subjects. Adverse events will be tabulated and presented with frequencies and percentages using NCI CTCAE version 4.0. Safety population consists of all subjects who receive at least one dose of study medication. The ORR will be estimated as the proportion of subjects who achieve a response (CR/PR) assessed by RECIST. The corresponding two-sided 95% exact confidence interval will be calculated assuming a binomial distribution. The efficacy evaluable population includes all subjects who receive at least one dose of study drug, have an adequate baseline disease assessment and at least one post-baseline response assessment.

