1.4 Nivolumab Combined with Ipilimumab in Renal Cell Carcinoma

The combination of nivolumab with ipilimumab is currently being studied in the Phase 1 study CA209016. Subjects with mRCC (favorable/intermediate MSKCC score; Karnofsky performance status $\geq 80\%$; untreated or any number of prior therapies) were randomized to receive nivolumab 3 mg/kg + ipilimumab 1 mg/kg (arm N3 + I1) or nivolumab 1 mg/kg + ipilimumab 3 mg/kg (arm N1 + I3) IV Q3W for 4 doses then nivolumab 3 mg/kg IV Q2W until progression/toxicity. The primary objective was to assess safety/tolerability; secondary objective was to assess antitumor activity. Subjects were randomized to N3 + I1 (n = 21) and N1 + I3 (n = 23). Most patients (n = 34; 77%) had prior systemic therapy (N3 + I1: 16; N1 + I3: 18). The confirmed ORR was 43% (N3 + I1) and 48% (N1 + I3). DOR was 4.1+ to 42.1+ wks (7 of 9 responses ongoing) in N3 + I1, and 12.1+ to 35.1+ wks (9 of 11 responses ongoing) in N1 + I3. Best response of SD was seen in 5 (24%) pts (N3 + I1) and 8 (35%) pts (N1 + I3). Median PFS was 36.6 wks (N3 + I1) and 38.3 wks (N1 + I3); with 11 of 21 events reported for N3 + I1 and 10 of 23 events reported for N1 + I3.¹⁷

The safety of nivolumab combined with ipilimumab was assessed in the Phase 1 study CA209016. Treatment-related AEs were seen in 39/44 pts (89%), including 16/21 (76.2%) in N3 + I1 and 23/23 (100%) in N1 + I3. Across the N3 + I1 and N1 + I3 arms, the most common ($\leq 20\%$) treatment related AEs of any grade were fatigue (61%), diarrhea (32%), nausea (30%), rash (27%), pruritis (25%), ALT increased (23%), AST increased (20%), hypothyroidism (20%), and asymptomatic lipase increased (20%). Grade 3–4 related AEs occurred in 19 pts (29%), including 6/21 (29%) at N3 + I1 and 14/23 (61%) at N1 + I3. The most common ($\geq 5\%$) drug-related Grade 3–4 events were asymptomatic lipase increased (21%), ALT increased (14%), AST increased (7%), diarrhea (9%), fatigue (5%), amylase increased (5%), colitis (5%), lymphocyte count decreased (5%). No grade 3–4 pneumonitis was seen. No treatment-related deaths were reported. Treatment-related AEs (including Grade 3–4), treatment-related AEs leading to discontinuation, and treatment-related SAEs all occurred more commonly in subjects in the N1 + I3 arm than in the N3 + I1.¹⁷

STU072016-044, [name], FormA-ResearchProtocol-V7.0-09.30.19, Mod_14, 10-23-19 (2)

Page 14 of 99 (BMS CA209-444) V. V6.0 date March 1, 2019

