This material is the property of the [UTSW Simmons Cancer Center](#). Do not disclose or use except as authorized in writing by the study sponsor.

Per a study amendment, the N3 + I1 and N1 + I3 arms were expanded to better evaluate safety and efficacy. Mature efficacy data was presented at ASCO 2015. The confirmed ORR was 38.3% (N3 + I1) and 40.4% (N1 + I3). Best response of SD was achieved in 36.2 % of patient in both treatment arms. Median DOR was 67.7 weeks (range 4.1+ to 91.1+) in the N3 + I1 arm and 81.1 weeks (range 6.1+ to 81.1+) in the N1 + I3 arm. Responses were durable, with >60% of patients continuing to experience ongoing response. The PFS rate (95% CI) at 24 weeks was 54% (39–68) in the N3 + I1 arm (N = 47) and 68% (52–79) in the N1 + I3 arm (N = 47). Median OS was not reached in either the N3 + I1 arm or in the N1 + I3.¹⁸

Table 1. ORR and best Overall Response

	NIVO3 + IPI1	NIVO1 + IPI3	NIVO3 + IPI3
	N = 47	N = 47	N = 6
Confirmed ORR ^a , n (%) 95% CI	18 (38.3) 24.5–53.6	19 (40.4) 26.4–55.7	0
Best overall response ^b , n (%)			
Complete response	4 (8.5)	1 (2.1)	0
Partial response	14 (29.8)	18 (38.3)	0
Stable disease	17 (36.2)	17 (36.2)	5 (83.3)
Progressive disease	10 (21.3)	7 (14.9)	1 (16.7)

^aConfirmed response only; ^bNo unconfirmed complete responses were reported in either arm; unconfirmed partial responses were reported in one patient (2.1%) in the NIVO3 + IPI1 arm and in two patients (4.3%) in the NIVO1 + IPI3 arm. Best overall response was not determinable in one patient (2.1%) in the NIVO3 + IPI1 arm and in two patients (4.3%) in the NIVO1 + IPI3 arm.

Grade 3–4 related AEs occurred in 36 pts, including 16/47 (34%) at N3 + I1 and 30/47 (63.8%) at N1 + I3. The most common (≥20%) drug-related Grade 3-4 events were lipase increased including 6/47 (12.8%) at N3 + I1 and 12/47 (25.5%) at N1 + I3; ALT increased including 2/47 (4.3%) at N3 + I1 and 4/47 (8.5%) at N1 + I3 and diarrhea including 1/47 (2.1%) at N3 + I1 and 7/47 (14.9%) at N1 + I3. Grade 3-4 colitis was observed in 6/47 (12.8) at N1 + I3 only. No grade 3–4 pneumonitis was seen. No treatment-related deaths were reported. Treatment-related AEs (including Grade 3-4), treatment-related AEs leading to discontinuation, and treatment-related SAEs all occurred more commonly in subjects in the N1 + I3 arm than in the N3 + I1 arm.¹⁸

Table 2. Treatment-related Select AEs^{a,b}

Category, n (%)	NIVO3 + IPI1		NIVO1 + IPI3		NIVO3 + IPI3	
	N = 47		N = 47		N = 6	

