2.3 Study Population

For entry into the study, the following criteria MUST be met.

2.3...1 Inclusion Criteria

Eligibility waivers are not permitted. Subjects must meet all of the inclusion and exclusion criteria to be registered to the study. Study treatment may not begin until a subject is registered

1) *Signed Written Informed Consent*

- Willing and able to provide informed consent

2) *Target Population*

- Histological confirmation of RCC with a clear-cell component
- Metastatic (AJCC Stage IV) RCC
- Prior adjuvant or neoadjuvant therapy for localized or locally advanced RCC is allowed provided recurrence occurred = or > 6 months after the last dose of the adjuvant or neoadjuvant therapy
- Any number of prior systemic treatment regimen in the advanced/metastatic setting is allowed (cytokine, anti-angiogenic, mTOR inhibitor or clinical trial) including previously untreated patients
- Karnofsky Performance Status (KPS) of at least 70%
- Life expectancy of at least 3 months
- At least 2 metastatic sites of which at least 1 must be measurable as per RECIST 1.1

- Archival Formalin-fixed paraffin-embedded (FFPE) tumor tissue must be available for correlative studies (Note: Fine Needle Aspiration [FNA] and bone metastases samples are not acceptable for submission)
- Patients with favorable, intermediate and poor risk categories will be eligible for the study. *Patients must be categorized according to favorable versus intermediate/poor risk status at registration. International Metastatic RCC Database Consortium (IMDC) must be used to determine prognostic factors (Appendix 1)*

2.3.2 Exclusion Criteria:

1) Target Disease Exceptions

- Subjects with previously treated brain or CNS metastases are eligible provided that the subject has recovered from any acute effects of radiotherapy and is not requiring steroids, and any whole brain radiation therapy was completed at least 4 weeks prior to study drug administration, or any stereotactic radiosurgery was completed at least 2 weeks prior to study drug administration. Liver metastases will not be included as part of the radiated lesions to be treated.

2) Medical History and Concurrent Diseases

- Prior treatment with an anti-PD-1, anti-PD-L1, anti-PD-L2, anti-CD137, or anti-CTLA-4 antibody, or any other antibody or drug specifically targeting T-cell co-stimulation or checkpoint pathways. Prior treatment with HD IL-2 is allowed.

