4.6.9 Evaluating best overall response

The best overall response is the best response recorded from the start of treatment until either disease progression or recurrence. The investigator's determination of best overall response will be based both on response criteria and on confirmation criteria. To be assigned a status of partial response or complete response, changes in tumor measurements must be confirmed by repeat assessment performed at least 6 weeks after the criteria for response are first met. To confirm stable disease, follow-up measurements must meet SD criteria at a minimum interval of 6 weeks after SD was first documented. Table 9 can be used as an assessment tool.

Table 9. Assessing Overall Response

Target Lesions	Non-target Lesions	New Lesions	Overall Response
CR	CR	No	CR
CR	Incomplete response/SD	No	PR
PR	Non-PD	No	PR
SD	Non-PD	No	SD
PD	Any	Yes or No	PD
Any	PD	Yes or No	PD
Any	Any	Yes	PD

Abbreviations: CR, complete response; PD, progressive disease; PR, partial response; SD, stable disease.

STU072016-044, [name], FormA-ResearchProtocol-V7.0-09.30.19, Mod_14, 10-23-19 (2)

Page 60 of 99 (BMS CA209-444) V. V6.0 date March 1, 2019

This material is the property of the [UTSW Simmons Cancer Center](#). Do not disclose or use except as authorized in writing by the study sponsor.

Patients with global deterioration of health status who require treatment to be discontinued without objective evidence of disease progression should be classified as having symptomatic deterioration. Every effort should be made to document their objective progression, even after discontinuing treatment.

Patients who do not have tumor response assessment due to rapid progression or toxicity will be considered non-responders, will be included in the denominator for the response rate, and will be classified into one of the categories listed below:

- death attributed to disease progression
- early discontinuation attributed to disease progression
- death attributed to drug toxicity
- early discontinuation attributed to drug toxicity

Note: If a patient receives subsequent therapy before tumor progression is documented, the reason for changing therapy must be reported. Reasons include clinical progression, drug toxicity, or secondary therapy for maintaining tumor response.

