9.3 Justification for the Sample Size

The point estimate of the ORR with nivolumab in combination with ipilimumab in this patient population is 40%, based on the Phase I presented at ASCO meeting which is chosen as the reference rate (P0) in the study proposed. The response rate where the regimen would be considered promising to pursue further is 70% (P1). In the first stage,

responses will be evaluated on the first 15 subjects treated. If 6 or fewer responses are observed after 6-18 weeks of follow-up, the study will be terminated for futility. Otherwise, 10 additional subjects will be accrued to target a total of 25 treated subjects. During the evaluation of response in the first stage, we will continue the recruitment and treatment of subjects. This design has at least a 90% chance (power) of concluding the combination therapy is effective when the true response rate is 70% and a 5% chance (Type I error) of concluding the treatment is effective when the true response rate is 40% or less. The probability of stopping early is 61% if the true response rate is 40% or less and 1.5% if the true response rate is 70%. The null hypothesis will be rejected and the regimen will be declared a success if at the end of the study 17 or more responses are observed in 25 treated subjects. The anticipated accrual rate for this group of patients is expected to be 2 patients per month.

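### Section 9.4 does not name the ORR denominator, and the only efficacy population it defines would drop unscanned patients and bias the reported ORR upward

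*Combined protocol and SAP*

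**What the plan says.** Section 9.4 assigns the safety analyses to all treated subjects. For efficacy it says only this: "The ORR will be estimated as the proportion of subjects who achieve a response (CR/PR) assessed by RECIST". It adds that "The corresponding two-sided 95% exact confidence interval will be calculated assuming a binomial distribution". No analysis population is attached to either sentence. The section then defines one efficacy population, made up of subjects who were dosed and who "have an adequate baseline disease assessment and at least one post-baseline response assessment". It does not say where that population is used.

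Two other sections bear on the denominator:

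- Section 4.6.9 gives an explicit rule on the response rate: "Patients who do not have tumor response assessment due to rapid progression or toxicity will be considered non-responders, will be included in the denominator".
- Section 9.3 sets both decisions on treated subjects. Stage 1 looks at the first 15 treated, and the regimen succeeds if "17 or more responses are observed in 25 treated subjects".

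The synopsis makes it a primary aim to estimate the ORR and compare it with reported nivolumab plus ipilimumab data. Section 9.3 takes its 40% reference rate from the Phase 1 study summarised in Section 1.4. The footnote to Table 1 there states: "Best overall response was not determinable in one patient (2.1%) in the NIVO3 + IPI1 arm".

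**The concern.** A patient who dies or stops before the first scan is outside the population defined in 9.4 but inside the denominator required by 4.6.9. Both cannot govern the same ORR, and nothing says which one takes precedence. Patients unscanned for other reasons, such as withdrawal or loss to follow-up, are not covered by the 4.6.9 rule at all, and the 9.4 definition leaves them out.

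The direction of the effect is fixed. Response requires a post-baseline assessment, so an excluded patient is never a responder. The numerator stays the same and the denominator shrinks.

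What is at stake is the published primary estimate and its comparison with the Phase 1 reference. If the choice stays open until the data are known, the denominator could be chosen after the result is seen.

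The population may also lose more patients early than the reference did. Section 1.4 describes the Phase 1 cohort as "favorable/intermediate MSKCC score; Karnofsky performance status" of at least 80%. This trial accepts a Karnofsky score of 70%, and "Patients with favorable, intermediate and poor risk categories will be eligible for the study".

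**Working it through.** **1. Which denominator does the reference use?** Table 1 in Section 1.4 reports 18 confirmed responses in 47 patients on the regimen used here, printed as 38.3% (24.5–53.6).

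- All 47 patients: 18/47 = 38.3%, Clopper–Pearson 95% CI 24.5–53.6. This matches the printed figures.
- Without the one not-determinable patient: 18/46 = 39.1% (25.1–54.6). This does not match.

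The reference therefore keeps the not-determinable patient in the denominator. An evaluable-only ORR in this trial would not be like for like with it.

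**2. Size of the shift.** Let f be the share of treated patients with no post-baseline assessment. None can be a responder, so reported ORR = true ORR / (1 − f). The documents give no f for this trial, so 2% to 16% is an assumed range. The low end is close to the Phase 1 not-determinable rate on this regimen, 1/47 = 2.1%. With a true ORR of 40% among treated patients:

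| Assumed f | Calculation | Reported ORR |
|---|---|---|
| 2% | 0.40/0.98 | 40.8% |
| 4% | 0.40/0.96 | 41.7% |
| 8% | 0.40/0.92 | 43.5% |
| 16% | 0.40/0.84 | 47.6% |

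**3. Effect on the exact interval.** Same number of responders, with 0, 1 or 2 of the 25 treated patients unassessed (Clopper–Pearson 95%):

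| Responders | All 25 treated | One excluded | Two excluded |
|---|---|---|---|
| 10 | 40.0% (21.1–61.3) | 41.7% (22.1–63.4) | 43.5% (23.2–65.5) |
| 15 | 60.0% (38.7–78.9) | 62.5% (40.6–81.2) | 65.2% (42.7–83.6) |
| 17 | 68.0% (46.5–85.1) | 70.8% (48.9–87.4) | 73.9% (51.6–89.8) |

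Both limits rise in every row. With 15 responders, one exclusion carries the lower limit past the 40% reference. With 17, one exclusion carries the estimate past the 70% target. The fewest responders that put the lower limit above 40% is 16 when the denominator is 25, and 15 when it is 24.

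**4. How likely is at least one such patient in 25?**

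- At 1/47, the rate on this regimen: 1 − (46/47)^25 = 0.416, about 42%.
- At 2/47, the rate in the other dose arm of Table 1: 1 − (45/47)^25 = 0.663, about 66%.

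**5. Effect on the decisions.** None. The 7-of-15 and 17-of-25 thresholds in Section 9.3 are counts of responders among treated subjects, and leaving a non-responder out of the reported proportion does not alter a count.

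**The case against.** The strongest reply is that the protocol, read as a whole, already favours all treated subjects. Section 4.6.9 is a direct denominator rule and Section 9.3 counts treated subjects, whereas the 9.4 population is defined but never applied. On that reading most early deaths and toxicity dropouts stay in, and only patients unscanned for other reasons are in doubt. That limits the likely size of the bias. It does not settle the point: 9.4 is the section that has to define the primary estimate, it does not refer to 4.6.9, and it leaves the residual group out.

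Several limits on the illustration are fair:

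- No rule in the plan compares the lower limit with 40% or the estimate with 70%. The crossings in step 3 affect how the result reads, not whether the trial succeeds. With 15 responders it misses its criterion under either denominator.
- The 2/47 rate comes from a dose arm that this trial does not use. A not-determinable best response is also only a proxy for having no post-baseline assessment, because Table 1 gives no reason.
- The 16% upper end is an assumption with no source in the documents.
- At 2% to 4% unassessed the shift is 0.8 to 1.7 points, against an interval about 40 points wide (10/25: 61.3 − 21.1 = 40.2).
- Higher early loss than in Phase 1 is plausible but not shown. Entry requires a life expectancy of at least 3 months, the first scan is due at 6 weeks, and scans continue through dosing interruptions.

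These points reduce the expected size. They leave the missing denominator, the conflict and the direction of the bias as they are.

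**Conclusion.** The concern holds and should be fixed. Section 9.4 names no denominator for a co-primary estimate. Its one efficacy population conflicts with 4.6.9, does not match the treated-subject basis of 9.3, and is more lenient than the Phase 1 reference.

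That this population would be used for the ORR is an inference from its place in the section, not a statement in the plan. If it is used, the upward bias is certain in direction whenever a treated patient is excluded. Its size depends on how many are unassessed, which the documents do not give. It is likely to be small at Phase 1 rates and reaches 7.6 points (47.6 − 40.0) at the top of the assumed range. The go/no-go rules are not affected.

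**What to change.** In Section 9.4, state that:

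- the primary ORR and its exact confidence interval use all subjects who receive any study drug, the same basis as the interim and final decisions in 9.3, and that unassessed subjects are not replaced;
- any such subject with no post-baseline assessment, for whatever reason, counts as a non-responder. This adopts the 4.6.9 rule and extends it to withdrawal, loss to follow-up and missed scans;
- the efficacy-evaluable population serves only a labelled sensitivity analysis.

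A cross-reference between 9.4 and 4.6.9 would keep the two aligned. The documents do not propose replacing subjects, so that clause only closes off a possible reading.

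The cost is one paragraph of wording, with no extra patients or data. The reported ORR may come out slightly less favourable.

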9.5 Statistical Analyses of Secondary Endpoints

Clinical Endpoints: Time-to-event outcomes (e.g., TTP, DOR, PFS, OS, local control of irradiated lesion) will be described using the Kaplan-Meier method. Median values will also be estimated with 95% confidence intervals.

Exploratory Correlative studies: Optional biopsies will be performed in all subjects at baseline (within 28 days prior to combination therapy) and during week 7 on therapy. Immune related biomarkers at baseline and post-therapy will be summarized with descriptive statistics and graphically displayed by exploratory plots. Frequencies and percentages will be presented for categorical variables. Changes will be estimated as a ratio change (post/pre) and data will be log transformed as appropriate to induce symmetry and stabilize the variability.

Difference between pre- and post-therapy will be explored using paired t-tests or nonparametric Wilcoxon signed rank tests for continuous variables and McNemar's test for dichotomous or categorical variables (e.g., proportion of subjects with marker-positive at pre- and post-therapy). Distributions of immune parameters across clinical responders and non-responders will be evaluated and graphically displayed using box plots. Differences of baseline and change in these parameters across tumor response groups will be explored using Jonckheere-Terpstra trend test, Wilcoxon rank sum test as well as logistic regression where appropriate.

10 Record Retention

11 Obligations of Investigators

13 APPENDIX 1 INTERNATIONAL METASTATIC RCC DATABASE CONSORTIUM (IMDC) PROGNOSTIC CRITERIA

Adverse Prognostic Factors

Clinical

KPS < 80%

Time from diagnosis to treatment < 1 year

Laboratory

Hemoglobin < LLN

Corrected calcium > ULN

Absolute neutrophil count > ULN

Platelet count > ULN

LLN = Lower limit of normal

ULN = Upper limit of normal

Corrected calcium (mg/dL) = measured total Ca (mg/dL) + 0.8 (4.0 - serum albumin[g/dL]), where 4.0 represents the average albumin level in g/dL.

Corrected calcium (mmol/L) = measured total Ca (mmol/L) + 0.02 (40 - serum albumin[g/L]), where 40 represents the average albumin level in g/L

Risk Group Based on Number of Adverse Prognostic Factors

Number of Adverse Prognostic Factors Present	Risk Group
0	Favorable
1-2	Intermediate
3-6	Poor

14 APPENDIX 2 MANAGEMENT ALGORITHMS FOR IMMUNO-ONCOLOGY AGENTS

A general principle is that differential diagnoses should be diligently evaluated according to standard medical practice. Non-inflammatory etiologies should be considered and appropriately treated.

[figure not shown]
Corticosteroids are a primary therapy for immuno-oncology drug-related adverse events. The oral equivalent of the recommended IV doses may be considered for ambulatory patients with low-grade toxicity. The lower bioavailability of oral corticosteroids should be taken into account when switching to the equivalent dose of oral corticosteroids.

Consultation with a medical or surgical specialist, especially prior to an invasive diagnostic or therapeutic procedure, is recommended.

The frequency and severity of the related adverse events covered by these algorithms will depend on the immuno-oncology agent or regimen being used.

GI Adverse Event Management Algorithm

[figure not shown]
Rule out non-inflammatory causes. If non-inflammatory cause is identified, treat accordingly and continue I-O therapy. Opiates/narcotics may mask symptoms of perforation. Infliximab should not be used in cases of perforation or sepsis.

Patients on IV steroids may be switched to an equivalent dose of oral corticosteroids (e.g. prednisone) at start of tapering or earlier, once sustained clinical improvement is observed. Lower bioavailability of oral corticosteroids should be taken into account when switching to the equivalent dose of oral corticosteroids.

Renal Adverse Event Management Algorithm

[figure not shown]
Rule out non-inflammatory causes. If non-inflammatory cause, treat accordingly and continue I-O therapy

Patients on IV steroids may be switched to an equivalent dose of oral corticosteroids (e.g. prednisone) at start of tapering or earlier, once sustained clinical improvement is observed. Lower bioavailability of oral corticosteroids should be taken into account when switching to the equivalent dose of oral corticosteroids.

Pulmonary Adverse Event Management Algorithm

[figure not shown]
Rule out non-inflammatory causes. If non-inflammatory cause, treat accordingly and continue I-O therapy. Evaluate with imaging and pulmonary consultation.

Patients on IV steroids may be switched to an equivalent dose of oral corticosteroids (e.g. prednisone) at start of tapering or earlier, once sustained clinical improvement is observed. Lower bioavailability of oral corticosteroids should be taken into account when switching to the equivalent dose of oral corticosteroids.

Hepatic Adverse Event Management Algorithm

Rule out non-inflammatory causes. If non-inflammatory cause, treat accordingly and continue I-O therapy. Consider imaging for obstruction.

[figure not shown]
Patients on IV steroids may be switched to an equivalent dose of oral corticosteroids (e.g. prednisone) at start of tapering or earlier, once sustained clinical improvement is observed. Lower bioavailability of oral corticosteroids should be taken into account when switching to the equivalent dose of oral corticosteroids.

*I-O therapy may be delayed rather than discontinued if AST/ALT ≤ 8 x ULN and T.bili ≤ 5 x ULN.

**The recommended starting dose for grade 4 hepatitis is 2 mg/kg/day methylprednisolone IV.

Endocrinopathy Management Algorithm

Rule out non-inflammatory causes. If non-inflammatory cause, treat accordingly and continue I-O therapy. Consider visual field testing, endocrinology consultation, and imaging.

[figure not shown]

Patients on IV steroids may be switched to an equivalent dose of oral corticosteroids (e.g. prednisone) at start of tapering or earlier, once sustained clinical improvement is observed. Lower bioavailability of oral corticosteroids should be taken into account when switching to the equivalent dose of oral corticosteroids.

onsor

Skin Adverse Event Management Algorithm

Rule out non-inflammatory causes. If non-inflammatory cause, treat accordingly and continue I-O therapy.

[figure not shown]

Patients on IV steroids may be switched to an equivalent dose of oral corticosteroids (e.g. prednisone) at start of tapering or earlier, once sustained clinical improvement is observed. Lower bioavailability of oral corticosteroids should be taken into account when switching to the equivalent dose of oral corticosteroids.

*Refer to NCI CTCAE v4 for term-specific grading criteria.

Neurological Adverse Event Management Algorithm

Rule out non-inflammatory causes. If non-inflammatory cause, treat accordingly and continue I-O therapy.

Patients on IV steroids may be switched to an equivalent dose of oral corticosteroids (e.g. prednisone) at start of tapering or earlier, once sustained clinical improvement is observed. Lower bioavailability of oral corticosteroids should be taken into account when switching to the equivalent dose of oral corticosteroids.
